13.4 Exploratory Efficacy Analyses

No planned exploratory efficacy analyses are defined.

14. SAFETY ANALYSES

All safety analyses including the analysis of plasma concentration data will be performed using the actual treatment for SAS1 in Stage 1 (5 weeks) and SAS2 in Stage 2 (5 weeks). To evaluate treatment differences in 10-week safety data, unless otherwise specified, safety data from Baseline (Study Week 0) to Study Week 10 will also be summarized by treatment group for subjects in SAS1 who were not randomized to the pimavanserin group in Stage 2.

For Stage 1, Baseline is Study Week 0 and Week 5 is Study Week 5. For Stage 2, Baseline is Study Week 5 and Week 5 is Study Week 10.

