3. STUDY DESIGN

3.1 General Study Design

This study is a multicenter, randomized, double-blind, placebo-controlled, 2-stage Sequential Parallel Comparison Design (SPCD) study in patients with MDD and an inadequate response to antidepressant therapy with concurrent SSRI/SNRI. MDD and Major Depressive Episode (MDE) are defined according to the Diagnostic and Statistical Manual of Mental Disorders, Fifth Edition (DSM-5), as confirmed by the Structured Clinical Interview for DSM-5, Clinical Trials Version (SCID-5-CT). Inadequate treatment response will be determined through the administration of the Massachusetts General Hospital Antidepressant Treatment Questionnaire (MGH ATRQ).

[figure not shown]
The study drug will be pimavanserin 34 mg (provided as 2×17 mg tablets) and matching placebo (2×placebo tablets), administered orally as a single dose once daily (QD).

The study duration is approximately 17 weeks consisting of a Screening Period of 8-21 days, a 10-week Treatment Period divided into 2 stages of equal 5-week durations, and a Safety Follow-up period of approximately 30 days. At the beginning of Stage 1 (Week 0), eligible subjects will be randomly assigned in a 1:3 ratio to pimavanserin or placebo, respectively. At the end of Stage 1 (Study Week 5), subjects initially randomized to placebo and who meet the non-responder criteria (i.e., HAM-D-17 total score at Week 5 >14 and percent-reduction from the Study Week 0 (Baseline) HAM-D-17 total score of <50%) will be randomly assigned in a 1:1 ratio to pimavanserin or placebo. Subjects who do not meet the criteria for re-randomization will continue with the assigned treatment from Stage 1 until the end of Stage 2. Subjects initially randomized to pimavanserin in Stage 1 will continue to receive pimavanserin through the end of Stage 2.

The study is a multicenter study with up to 30 study sites participating. Approximately 188 adult male and female patients with MDD are expected to participate in this study.

The study design is summarized in Figure 1.

Figure 1 Schematic of Study Design

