3.3.2 Stage 2 Double-blind Treatment Period

At the end of Stage 1 (Study Week 5), subjects initially randomized to placebo and who meet the non-responder criteria will be randomly assigned in a 1:1 ratio to pimavanserin or placebo. Subjects initially randomized to pimavanserin in Stage 1 will continue to receive pimavanserin through the end of Stage 2.

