3.5 Determination of Sample Size

The primary efficacy endpoint is the change from Baseline to Week 5 in the Hamilton Depression Scale (17 Items) (HAMD-17) total score. For Stage 1, Baseline is Study Week 0 and Week 5 is Study Week 5. For Stage 2, Baseline is Study Week 5 and Week 5 is Study Week 10.

A total sample size of 168 evaluable subjects is estimated to provide at least 80% power at a two-sided significance level of 0.05 assuming a mean change in the HAMD-17 total score of -7.8 (SD=8) and -10 (SD=8) in Stage 1, and -2.8 (SD=6) and -6.0 (SD=6) in Stage 2 for the placebo and pimavanserin groups, respectively.

For the above calculation, the weight for each double-blind treatment stage is equal to 0.5 and it is assumed that approximately 70% of placebo subjects will be non-responders at the end of Stage 1.

Adjusting for a potential non-evaluable rate of up to 10%, approximately 188 subjects will be randomized into Stage 1 (47 to pimavanserin and 141 to placebo). It is anticipated that approximately 98 subjects will be randomized into Stage 2 (49 to pimavanserin and 49 to placebo).

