10. EXTENT OF EXPOSURE AND TREATMENT COMPLIANCE

Extent of exposure and treatment compliance will be summarized as continuous variables by treatment group for SAS1 in Stage 1 (5 weeks), SAS2 in Stage 2 (5 weeks), and the subjects in SAS1 who were not randomized to the pimavanserin group in Stage 2 (10 weeks).

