10.1 Exposure to Study drug

Duration of exposure to study drug will be calculated for each subject as (last dose date – first dose date + 1).

For SAS1 and SAS2, the number and percentage of subjects within each of the following exposure levels (a maximum of 5 weeks [approximately 35 days]) in terms of duration (days) of exposure will also be tabulated: ≤ 10 , 11- ≤ 20 , 21- ≤ 30 , and > 30 . For the PIM subjects vs. the placebo subjects in SAS1 who were not randomized to the pimavanserin group in Stage 2, the exposure levels will be: ≤ 20 , 21- ≤ 40 , 41- ≤ 60 , and > 60 . Kaplan-Meier curves of duration on study drug will also be presented for each treatment group.

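### The 10-week by-treatment summaries remove about half of the placebo non-responders and no Stage 1 pimavanserin subjects, so the placebo column is not a randomized comparator

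*SAP*

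**What the plan says.** SAP section 14 assigns safety analyses to SAS1 in Stage 1 and SAS2 in Stage 2. It then adds a Week 0 to Week 10 summary, introduced with the words "To evaluate treatment differences in 10-week safety data", in which data are "summarized by treatment group for subjects in SAS1 who were not randomized to the pimavanserin group in Stage 2".

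The design determines who is removed. Under SAP section 3.3.2, "subjects initially randomized to placebo and who meet the non-responder criteria will be randomly assigned in a 1:1 ratio to pimavanserin or placebo". Under section 3.1, "Subjects initially randomized to pimavanserin in Stage 1 will continue to receive pimavanserin through the end of Stage 2". A subject assigned to pimavanserin in Stage 2 is therefore always a Stage 1 placebo subject who was a Week 5 non-responder.

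The same selection recurs:
- exposure and compliance (section 10: "the subjects in SAS1 who were not randomized to the pimavanserin group in Stage 2 (10 weeks"), with section 10.1 setting the two groups against each other ("For the PIM subjects vs. the placebo subjects in SAS1 who were not randomized to the pimavanserin group in Stage 2");
- efficacy summary statistics (section 12, based on FAS1, with no comparative purpose stated);
- C-SSRS, AIMS, BARS and the Simpson Angus Scale (section 14.6).

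The SAP attaches no weight or caveat to these tables. Table specifications are in a separate document that was not available, so a footnote may exist there. Protocol section 9.4.1 describes a different both-stage set: only subjects not eligible for re-randomization, which leaves out every re-randomized placebo non-responder. SAP section 19 reports no change from the protocol.

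**The concern.** Removal from the 10-week set depends on an outcome measured after randomization and happens in one arm only. The placebo column is enriched for responders and for subjects who left before Week 5. The pimavanserin column is the whole Stage 1 arm, whatever its response. A difference between the columns therefore mixes treatment with selection.

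The distortion has two directions. Events associated with persistent non-response are under-counted on placebo. Events that can occur only in subjects who leave before Week 5, such as Stage 1 TEAEs leading to discontinuation or the shortest exposure category, are over-counted, because all those subjects stay while the denominator shrinks. A reader cannot correct for this by eye. In the 10-week efficacy summary the placebo change looks better than it was, which works against the drug.

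**Working it through.** **Inputs (SAP section 3.5).** 188 randomized (47 pimavanserin, 141 placebo); "approximately 98 subjects will be randomized into Stage 2 (49 to pimavanserin and 49 to placebo"; 70% placebo non-response; Stage 1 change of -7.8 on placebo and -10 on pimavanserin (SD 8); Stage 2 change of -2.8 and -6.0 (SD 6); a non-evaluable allowance of 10%.

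**The plan's figures reproduce.**
- Weighted effect: 0.5 × 2.2 + 0.5 × 3.2 = 2.7.
- Variance with 168 evaluable: 0.25 × 64 × (1/42 + 1/126) + 0.25 × 36 × (2/44.1) = 0.916. So z = 2.7/0.957 = 2.82 and power is 0.805.
- 168/0.9 = 186.7, and 188 is the next multiple of 4 above it. 0.70 × 141 = 98.7, against 98 stated.

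**Composition of the 10-week set.**
- Placebo: 141 - 49 = 92 kept. Pimavanserin: 47 of 47 kept.
- Re-randomized non-responder share: 98/141 = 69.5% before, 49/92 = 53.3% after.

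**1. Events tied to non-response.** The shift is a factor times the non-responder minus responder risk difference.
- No early leavers: 43/92 - 43/141 = 0.162.
- 14 of the 43 others leave early and resemble non-responders: 29/92 - 29/141 = 0.110.
- 10% leave first and 70% of the rest are re-randomized: 127 reach Week 5, 89 are non-responders, 44.5 are removed and 96.5 are left. The factor is 38/96.5 - 38/141 = 0.124.

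The documents do not give the risk difference. An assumed 5 to 20 points gives a shift of about 0.5 to 3.2 points. For scale, one of 47 pimavanserin subjects is 2.1 points.

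**2. Events confined to subjects who leave before Week 5.** Inflation is 141/92 = 1.53, or 141/96.5 = 1.46 if the 10% allowance is taken as early leavers. With an assumed 5 such placebo subjects, the true 5/141 = 3.5% would appear as 5/96.5 = 5.2% to 5/92 = 5.4%.

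**3. Observed placebo HAMD-17 change at Study Week 5.** Assume normality and split a distribution with mean -7.8 and SD 8 at 30/70. Responders average -17.07 and non-responders -3.83, a gap of 13.25.
- Exact 70% non-response: (0.30/0.65 - 0.30) × 13.25 = 0.1615 × 13.25 = 2.14 points.
- 14 leavers without a Week 5 score and 98 re-randomized: (29/78 - 29/127) × 13.25 = 0.1435 × 13.25 = 1.90 points.
- Simulating the actual rule (score above 14 and reduction below 50%) with an assumed baseline mean of 26 to 28, SD 3.5 to 5 and baseline-change correlation 0 or -0.3 gives 66% to 76% non-responders and shifts of 1.8 to 2.0 points.
- In 20,000 simulated trials with no drug effect, using the 30/70 split, the unweighted difference averaged 2.10 points against pimavanserin. After weighting it was -0.01.

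**At Study Week 10**, non-responders staying on placebo change by a further -2.8. The shift is the factor times (10.45 - d), where d is the responders' later change. An assumed d = +6 gives 0.64 to 0.72; d = -2.8 gives 1.90 to 2.14.

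**The case against.** The strongest reply is that these are supplementary descriptive tables. Randomized comparisons are already planned in SAS1/SAS2 and FAS1/FAS2, disposition (SAP section 6) uses the full sets, serious events and discontinuations are listed by subject, and no test uses the 10-week set. All of that stands and limits the severity. Against it, the SAP itself gives evaluating treatment differences as the purpose of the 10-week safety tables.

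Second, subjects switched to pimavanserin have no 10-week placebo course, so they must be left out or censored. That is true. The fault is that their share of the placebo arm is not replaced.

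Third, part of the removed subjects' Stage 1 data is shown elsewhere. Sections 12 and 14.6 plan Week 0 to Week 5 summaries for FAS2 efficacy and the SAS2 safety questionnaires. This is only a partial answer: sections 14.1 to 14.5 plan no such split for TEAEs, laboratory, vital-sign or ECG data.

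Fourth, much of the size is assumed. The risk differences are not in the documents, and the 0.110 factor and 1.90 figure imply 98/127 = 77% non-response rather than 70%. This stands as a caution, but the values consistent with 70% (0.124 and 2.14) lie inside the ranges given.

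Finally, a weighted column counts some rare events twice and does not address medians or extremes, and the safety sets classify by actual treatment while the weight comes from randomized allocation. These are fair reasons to keep the raw counts as they are and make the weighted figures an addition.

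**Conclusion.** The concern holds. As written, the 10-week placebo column is selected on Week 5 outcome and the pimavanserin column is not. The change in non-responder share from 69.5% to 53.3% follows from the planned counts alone. The safety shifts rest on an assumed risk difference (about 0.5 to 3.2 points) or on assumed early departures (inflation of 1.46 to 1.53). They run in opposite directions, so the net effect on any one event is unknown. The HAMD-17 shift of about 1.8 to 2.1 points at Week 5, against a planned Stage 1 effect of 2.2, rests on a normal model. The Week 10 range of 0.6 to 2.1 depends wholly on the assumed later course of responders.

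The problem is minor to moderate but worth fixing, because the repair is cheap. The difference from protocol section 9.4.1 is a separate documentation gap. The protocol set is more selected than the SAP set, so reverting to it would not help.

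**What to change.** In the 10-week summaries under SAP sections 10, 12 and 14:
- Keep the raw counts. Beside them, give percentages and means with weight 2 for placebo non-responders re-randomized to placebo and weight 1 for everyone else. The weight is the inverse of the known 1/2 chance of staying on placebo, and 43 + 2 × 49 = 141 restores the Stage 1 placebo arm. In the discontinuation example, 5/141 = 3.5% is recovered.
- Read individual SAE and suicidality events from the raw counts.
- Footnote that the unweighted columns are not a randomized comparison, and point to the stage tables.
- Reconcile the set with protocol section 9.4.1 and list the difference in SAP section 19.

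The per-treatment counting in SAP section 11 (concomitant medication) can stay, but extending it to TEAEs would not replace a 10-week comparison. It would set 47 + 49 = 96 pimavanserin subjects, 51% of them placebo non-responders with at most 5 weeks on drug, against 141 placebo subjects. Mean planned exposure would be (47 × 10 + 49 × 5)/96 = 7.4 weeks against (92 × 10 + 49 × 5)/141 = 8.3 weeks, ignoring dropout.

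The cost is SAP wording, one weight variable, one column and a footnote. Effective placebo size falls from 92 to 141²/(43 + 4 × 49) = 83, so standard errors rise by about 5%. Rare events in re-weighted subjects count double in the weighted column. The removed subjects' Stage 1 TEAE, laboratory, vital-sign and ECG data would still appear only in the SAS1 Stage 1 tables.

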14.1 Adverse Events

Adverse events will be coded using MedDRA dictionary, Version 19.0 or newer.

An AE (classified by preferred term) will be considered a treatment-emergent AE (TEAE) if started after first study dose administration and no later than last study dose date + 30. AEs reported on Day 1 based on Baseline (pre-dose) findings (e.g. clinically significantly abnormal vital signs, laboratory test results, or electrocardiogram parameters) will not be considered as TEAEs.

TEAEs will be classified into 2 stages for the summary of TEAEs by stage. If the onset date of a TEAE is on or after the Stage 2 randomization date or the Study Week 5 visit date for those who were not randomized into Stage 2, the TEAE will be assigned to Stage 2; else it will be assigned to Stage 1.

The number and percentage of subjects reporting TEAEs in each treatment group will be tabulated by system organ class (SOC) and preferred term; by SOC, preferred term, and maximum severity. The number and percentage of subjects reporting related TEAEs in each treatment group will also be tabulated by SOC and preferred term. If more than 1 AE occurs with the same preferred term for the same subject, then the subject will be counted only once for that preferred term using the most severe and most related occurrence for the summarization by severity and by relationship to study drug.

TEAEs will also be tabulated by treatment group and without displaying the SOC terms; this table will be sorted in descending order of frequency of preferred term within the pimavanserin group.

The incidence of most frequently reported (preferred terms reported by $\geq 5\%$ of subjects in any treatment group) TEAEs for Stages 1 and 2 only, treatment emergent SAEs, and TEAEs leading to discontinuation of study drug will be summarized by SOC, preferred term, and treatment group. The tables will be sorted alphabetically by SOC and then by descending

Statistical Analysis Plan
2018

21 August

order of subjects frequency within the pimavanserin group. In addition, the incidence of fatal treatment-emergent AEs (i.e., events that cause death) will be summarized separately by preferred term and treatment group.

An AE listing by subject will display all events, including those which occur during screening, and will include the verbatim term in addition to the MedDRA SOC and preferred term. This listing will also include all relevant eCRF data associated with the event: date of onset, date resolved, date of last dose, severity, frequency, outcome, relationship to study drug, and action taken with study drug. Separate listings will be presented for subjects with treatment-emergent SAEs, subjects with TEAEs leading to discontinuation and subject who died (if any).

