Subjects will complete the following procedures:

- Vital signs (sitting [at least 3 minutes] BP, pulse, respiratory rate, and temperature)
- Weight
- PK blood draw for pimavanserin, AC-279, and concomitant SSRI/SNRI levels
- Assessment of concomitant medications
- Assessment of AEs
- Scales listed in [Table 2](#) (HAM-D-17, CGI-S and I, SDS, KSS, BIS-11, SIS, C-SSRS)
 - The C-SSRS time frame is since last visit
- Study drug accountability
- Dispense study drug

6.5.6 Week 4

Subjects will complete the following procedures:

- Vital signs (sitting [at least 3 minutes] BP, pulse, respiratory rate, and temperature)
- Weight
- Assessment of concomitant medications
- Assessment of AEs
- Scales listed in [Table 2](#) (HAM-D-17, CGI-S and I, SDS, KSS, C-SSRS)
 - The C-SSRS time frame is since last visit
- Study drug accountability
- Dispense study drug

6.5.7 Week 5

Subjects will complete the following procedures:

- Physical examination
- Vital signs (sitting [at least 3 minutes] BP, pulse, respiratory rate, and temperature)
- Weight

- 12-lead ECG (single recording; before blood sampling or at least 30 minutes after blood sampling)
- Clinical laboratory tests
- Serum and urine pregnancy tests for women of childbearing potential
- Urine toxicity screen (done by central lab)
- PK blood draw for pimavanserin, AC-279, and concomitant SSRI/SNRI levels
- Assessment of concomitant medications
- Assessment of AEs
- Scales listed in [Table 2](#) (HAMD-17, CGI-S and I, SF-12, SDS, DAI-10, MGH-SFI, KSS, BIS-11, SIS, C-SSRS, AIMS, BARS, and SAS)
 - The C-SSRS time frame is since last visit
- Study drug accountability
- Re-randomization (see [Section 9.6.2.2](#))
- Dispense study drug

6.5.8 Week 6

Subjects will complete the following procedures:

- Vital signs (sitting [at least 3 minutes] BP, pulse, respiratory rate, and temperature)
- Weight
- 12-lead ECG (single recording; before blood sampling or at least 30 minutes after blood sampling)
- PK blood draw for pimavanserin, AC-279, and concomitant SSRI/SNRI levels
- Assessment of concomitant medications
- Assessment of AEs
- Scales listed in [Table 2](#) (HAMD-17, CGI-S and I, SDS, KSS, BIS-11, SIS, C-SSRS, AIMS, BARS, and SAS)
 - The C-SSRS time frame is since last visit
- Study drug accountability
- Dispense study drug

6.5.9 Week 7

Subjects will complete the following procedures:

- Vital signs (sitting [at least 3 minutes] BP, pulse, respiratory rate, and temperature)

- Weight

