7.2.2.1 Duration

The start and stop dates for AEs will be recorded using the following criteria:

- Start: Date of the first episode of the AE or date of significant sustained worsening in severity
- Stop: Date when AE either ceased permanently or changed in severity

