9.6.2.2 Stage 2 Double-blind Treatment Period

At the end of Stage 1 (Week 5), subjects initially randomized to placebo and who have met the predefined non-responder criteria (i.e., HAMD-17 total score at Week 5 >14 and percent-reduction from the Week 0 (Baseline) HAMD-17 total score of $<50\%$) are randomly assigned (1:1) to pimavanserin 34 mg or placebo. The determination of the subject's status and eligibility for randomization in the Stage 2 will be made in the double-blind manner via the IRT system. Subjects who do not meet criteria for randomization into Stage 2 will continue with the assigned treatment from Stage 1 for an additional 5 week period (until the end of the study double-blind treatment).

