3.4 Blinding

This is a double-blind study. Blinding is achieved by means of identical appearance for pimavanserin and placebo. Neither the subjects nor the study personnel at the clinical sites will know which treatment is administered to each subject.

All subjects and study personnel will be blinded to the randomization into Stage 2 of the study or continuation of the treatment. From the perspective of study subjects and investigators, the study will be conducted as a seamless 10-week double-blind treatment period.

Unplanned unblinding of treatment assignment during the study is discouraged. The investigator at a site may break the blind in the event of an immediate medical emergency, where knowledge of the subject's treatment assignment (pimavanserin or placebo) must be known in order to facilitate appropriate emergency medical treatment. The Investigator must

Statistical Analysis Plan
2018

21 August

first attempt to contact the study Medical Monitor before unblinding a subject's treatment identity in order to obtain concurrence that unblinding a subject's treatment assignment is necessary.

For the final analysis, the treatment codes for all subjects will be released to ACADIA after all subjects have completed the study and the clinical database is locked.

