4. ANALYSIS SETS

Randomized Analysis Sets

Randomized Analysis Set for Stage 1 – The Randomized Analysis Set for Stage 1 (RAS1) will consist of all subjects who were randomized into Stage 1.

Randomized Analysis Set for Stage 2 – The Randomized Analysis Set for Stage 2 (RAS2) will consist of all subjects who were placebo non-responders from Stage 1 and who were randomized into Stage 2.

Subjects will be classified according to the randomized treatment assignment.

Safety Analysis Sets

Safety Analysis Set for Stage 1 – The Safety Analysis Set for Stage 1 (SAS1) will consist of all subjects who were randomized into Stage 1 and received at least one dose of study drug in Stage 1.

Safety Analysis Set for Stage 2 – The Safety Analysis Set for Stage 2 (SAS2) will consist of all subjects who were placebo non-responders from Stage 1, were randomized into Stage 2, and received at least one dose of study drug in Stage 2.

Subjects will be classified according to the actual treatment received.

Full Analysis Sets

Full Analysis Set for Stage 1 – The Full Analysis Set for Stage 1 (FAS1) will consist of all subjects who were randomized into Stage 1, received at least one dose of study drug in Stage 1, and have both a Baseline (Study Week 0) value and at least one post-Baseline value for the HAMD-17 total score in Stage 1.

Full Analysis Set for Stage 2 – The Full Analysis Set for Stage 2 (FAS2) will consist of all subjects who were placebo non-responders from Stage 1, were randomized into Stage 2, received at least one dose of study drug in Stage 2, and have both a Baseline (Study Week 5) value and at least one post-Baseline value for the HAMD-17 total score in Stage 2.

Subjects will be classified according to the randomized treatment assignment.

Per-protocol Analysis Sets

Per-protocol Analysis Set for Stage 1 – The Per-protocol Analysis Set for Stage 1 (PAS1) will consist of a subset of subjects in FAS1 who do not have any protocol deviation which is considered to have substantial impact on the primary efficacy outcome. The precise reasons

Statistical Analysis Plan
2018

21 August

for excluding subjects from PAS1 will be fully defined and documented *a priori* before the clinical database lock.

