5.3 Analysis Visit Windows

Baseline for Stage 1 of the study is defined as the last non-missing result, including results from repeated and unscheduled measurements, before first dosing in Stage 1. Baseline for subjects randomized into Stage 2 is defined as the results at Study Week 5.

Statistical Analysis Plan
2018

21 August

Efficacy, safety, and PK assessments will be summarized by analysis visit as presented in Table 2 below. For the Week 5 visit window only, the assessments collected on the date of randomization for the subjects who are randomized into Stage 2 will be selected for the analysis even if the Stage 2 randomization date is outside of the Study Day Interval, 33 - 39.

Table 2 Analysis Visit Windows

Analysis Visit	Study Visit	Target Study Day @	Study Day Interval
Baseline (Day 1 for Stage 1)	2 (Week 0)	1	≤ 1
Week 1	3 (Week 1)	8	2 – 11
Week 2	4 (Week 2)	15	12 – 18
Week 3	5 (Week 3)	22	19 – 25
Week 4	6 (Week 4)	29	26 – 32
Week 5	7 (Week 5)	36	33 – 39
Week 6	8 (Week 6)	43	40 – 46
Week 7	9 (Week 7)	50	47 – 53
Week 8	10 (Week 8)	57	54 – 60
Week 9	11 (Week 9)	64	61 – 67
Week 10	12 (Week 10)	71	68 – 78
Follow-up	~30-Day Follow-Up	101	≥79

@ Derivation of study day: study day = assessment date - first dose date + 1 if the assessment date ≥ first dose date, otherwise study day = assessment date – first dose date. Study day 1 is the day of first administration of study drug (pimavanserin or placebo).

Efficacy and safety assessments for Stages 1 and 2, when presented side by side or separately, will be summarized by analysis visit as presented in Table 3.

Table 3 Analysis Visit for Side-by-side or Separate Presentation of Stages 1 and 2

Data

Analysis Visit	Study Visit in Stage 1	Study Visit in Stage 2
Baseline (Day 1)	2 (Week 0)	7 (Week 5)
Week 1	3 (Week 1)	8 (Week 6)
Week 2	4 (Week 2)	9 (Week 7)
Week 3	5 (Week 3)	10 (Week 8)
Week 4	6 (Week 4)	11 (Week 9)
Week 5	7 (Week 5)	12 (Week 10)

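### AEs arising from the Week 5 assessments are left out of the Stage 1 TEAE table in both arms, and for subjects then switched to pimavanserin they are never counted under placebo (minor; descriptive safety counts only)

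*SAP*

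**What the plan says.** SAP 14.1 splits TEAEs between stages by onset date: "If the onset date of a TEAE is on or after the Stage 2 randomization date or the Study Week 5 visit date" (the visit date applying to subjects not randomised into Stage 2), the event is assigned to Stage 2, and otherwise to Stage 1. The boundary date itself is always Stage 2.

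SAP 14 builds the stage tables on SAS1 for Stage 1 and SAS2 for Stage 2. On the latter, SAP 4 says: "The Safety Analysis Set for Stage 2 (SAS2) will consist of all subjects who were placebo non-responders from Stage 1", with the further conditions of re-randomisation and a Stage 2 dose. Everyone else stays on the same drug: "Subjects who do not meet criteria for randomization into Stage 2 will continue with the assigned treatment from Stage 1" (Protocol 9.6.2.2). SAP 14 adds a 10-week summary of SAS1 that leaves out subjects re-randomised to pimavanserin.

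The Week 5 visit closes Stage 1 and also opens Stage 2: "Baseline for subjects randomized into Stage 2 is defined as the results at Study Week 5" (SAP 5.3). Protocol 6.5.7 lists the Week 5 examination, vital signs, ECG, laboratory tests and scales ahead of re-randomisation and dispensing. SAP 14.1 excludes AEs based on pre-dose Baseline findings on Day 1, but does not say whether this extends to the Stage 2 Baseline.

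**The concern.** A finding made at the Week 5 visit reflects five weeks of Stage 1 treatment, yet the date rule hands the AE recorded from it to Stage 2. Week 5 is also Stage 1's only scheduled post-baseline visit for laboratory tests and physical examination, so an AE first detected by either and dated to that visit cannot enter the Stage 1 TEAE table. That table is the only TEAE comparison covering all subjects randomised at the start.

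Two consequences follow. Subjects not re-randomised are outside SAS2, so their boundary-date events fall between the two stage tables. Subjects who change from placebo to pimavanserin can have a finding that arose on placebo attributed to pimavanserin. With 47 planned pimavanserin subjects in Stage 1, single events are visible in the percentages.

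**Working it through.** **Planned numbers (SAP 3.5).** The plan's own counts reproduce. 168/(1 − 0.10) = 186.7, and the next multiple of four for 1:3 allocation is 188, giving 188/4 = 47 and 141, as stated: "approximately 188 subjects will be randomized into Stage 1 (47 to pimavanserin and 141 to placebo"). At 70% non-response, 0.70 × 141 = 98.7, against the stated 98 (49 + 49).

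**Where a Week 5-dated TEAE goes,** when re-randomisation is on the visit date:

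| Subjects | Planned n | Stage 1 table | Stage 2 table | 10-week summary |
|---|---|---|---|---|
| Pimavanserin throughout | 47 | no | no (not in SAS2) | yes, pimavanserin |
| Placebo, not re-randomised | 141 − 98 = 43 | no | no (not in SAS2) | yes, placebo |
| Placebo, then placebo | 49 | no | yes, placebo | yes, placebo |
| Placebo, then pimavanserin | 49 | no | pimavanserin, or not a TEAE | excluded |

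The first two rows are also absent from the table of TEAEs in at least 5% of subjects, which SAP 14.1 plans for the two stages only. All events remain in the AE listing.

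**The last row** depends on what Day 1 means in the pre-dose exclusion.
- The footnote to SAP Table 2 ties study day 1 to the first administration of study drug. On that reading the exclusion does not reach Week 5, and the finding counts under Stage 2 pimavanserin.
- SAP Table 3 attaches the Day 1 label to Baseline in both stages. On that reading the finding is dropped as a TEAE.

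Neither reading returns it to placebo. SAP 11 plans a 10-week table by treatment taken for concomitant medications, but SAP 14.1 plans none for TEAEs.

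**What is not touched.** Protocol 7.2.2.1 defines AE start as "Date of the first episode of the AE or date of significant sustained worsening in severity". Events that began before the boundary date stay in Stage 1.

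**Size.**
- Not re-randomised: 47 + 43 = 90 of 188 (47.9%). These are subjects the rule could reach, not subjects with an event.
- If 10% left before Week 5 (the plan's non-evaluable rate, borrowed as an assumption): 47 × 0.9 = 42.3, 43 × 0.9 = 38.7 and 49 × 0.9 = 44.1.
- One subject is 1/47 = 2.1 percentage points in Stage 1 pimavanserin, 1/141 = 0.7 in Stage 1 placebo and 1/49 = 2.0 in a Stage 2 arm. In the Stage 1 pimavanserin arm the 5% threshold lies between 2/47 = 4.3% and 3/47 = 6.4%, so one event can decide whether a term is listed.
- Illustration only, assuming 1% to 5% of subjects have such an event: 0.47 to 2.35 of 47, 0.43 to 2.15 of 43 and 0.49 to 2.45 of 49.

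**Check on a simpler remedy.** Suppose only subjects not re-randomised had their boundary moved to the day after the visit. Other Week 5-dated events, such as a spontaneously reported headache, would then count in Stage 1 for 47/47 = 100% of pimavanserin but 43/141 = 30.5% of placebo subjects. If such events occurred in 1% to 5% of each arm, the table would show 1.0% against 0.3%, up to 5.0% against 1.5%: an artificial difference of 0.7 to 3.5 points.

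**The case against.** A reader might infer from 100% against 30.5% that the present rule biases the Stage 1 comparison between arms. It does not: the Stage 1 table omits the boundary date for everyone who reaches it, in both arms. Those percentages describe only who lacks a stage table afterwards.

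A reader might also infer that the events are lost. They are not. Protocol 9.4.1 promises summaries across both stages for subjects not eligible for re-randomisation, and SAP 14 delivers them as the 10-week summary. The Week 5 laboratory, vital-sign, ECG and examination results are themselves tabulated for SAS1 as Stage 1 Week 5 data (SAP 14.2 to 14.5, with Table 3). What moves is the AE, not the abnormal value.

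A third argument is that assigning same-day events to the incoming drug is a reasonable convention. Onset is recorded as a date only, and SAP 5.6 similarly treats an unclear order as treatment-emergent. That stands for events whose order relative to the first Stage 2 dose is unknown. It is weaker for findings from the Week 5 assessments. Protocol 6.5.7 lists those before dispensing and, unlike the Baseline visit, specifies no dose in the clinic. The list is not stated to be a mandatory sequence, so some judgement remains.

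Finally, for re-randomised subjects the boundary is the Stage 2 randomisation date. If that fell after the visit, a visit-date event would stay in Stage 1 as it should.

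**Conclusion.** The point holds as a minor one. AEs arising from the Week 5 assessments miss the Stage 1 TEAE table in both arms. For the planned 90 subjects not re-randomised, such events reach only the 10-week summary and the listings. For the planned 49 switched to pimavanserin, such events are never counted under placebo, provided re-randomisation is on the visit date.

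The documents do not support a claim of bias between arms in the current Stage 1 table, of lost data, or of any effect on efficacy. The counts are descriptive and confined to one calendar date per subject. Their number cannot be derived; about 0 to 2 subjects per group rests on the assumed 1% to 5%.

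**What to change.** Add one rule to SAP 14.1, applied identically to every subject whatever the arm or re-randomisation status:

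> An AE with onset on the Stage 2 randomization date (or the Study Week 5 visit date for those not randomized into Stage 2) that is based on Week 5 assessments made before the first Stage 2 dose is assigned to Stage 1 as a TEAE under the Stage 1 treatment. The Day 1 exclusion applies to study day 1 only. All other TEAEs with onset on that date keep the present Stage 2 assignment.

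Do not give subjects who are not re-randomised a different date boundary, because that would create the imbalance shown in the check above.

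Identify the events by blinded review before database lock and flag them in the AE listing. Review the Week 5-dated AEs of all subjects, since re-randomisation status would reveal Stage 1 placebo and SAP 3.4 protects it: "All subjects and study personnel will be blinded to the randomization into Stage 2 of the study or continuation of the treatment".

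The cost is SAP wording, some programming and a short review. The drawback is reviewer judgement: the record holds an onset date without a time, and the listing fields in SAP 14.1 include no link to an assessment. Other same-date events may still be misplaced.

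Separately, SAP 7 assigns a major deviation to Stage 2 if it occurs or is identified on or after the boundary date. An entry breach found late in a subject outside RAS2 is then missing from both stage summaries. Assign deviations by date of occurrence, with eligibility deviations in Stage 1.
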